All participants will have two catheters, a venous and arterial, placed prior to the start of the PET scan. The first venous catheter will be inserted into a vein of one arm for the injection of the radiotracer. The arterial catheter will be inserted into a radial artery of the other arm by an anesthesiologist for rapid withdrawal of blood specimens for analysis of radiotracer. The wrist of each participant will be infiltrated intradermally via a 30 gauge needle with 2 mL 1% (20 mg (0.3 mg/kg for most adults) lidocaine hydrochloride before the insertion of the arterial line to provide local anesthesia. If participants experience discomfort at the site of insertion of the arterial line, then they will be administered subcutaneous injections of 2 mL 1% (20 mg (0.3 mg/kg for most adults) lidocaine hydrochloride. This dose corresponds to 10% of the maximal recommended dose and 5% of the dose associated with effects on the central nervous system. During the PET scan, up to forty blood samples (a total blood volume of approximately 150 mL) will be collected for metabolite and radioactivity analysis of the radiotracer.

(v)Transmission and emission scan:

After the catheters are placed the participant will be placed in the PET scanner and complete a 6 to 10 minute transmission (attenuation) scan performed before or after the PET scan. The participant will then have the PET scan performed during which an intravenous injection of approximately 20 mCi of [¹¹C]-OMAR will be administered. Dynamic PET data will be acquired during scanning for approximately 90 minutes following tracer injection.

b. Study duration and number of study visits required of research participants.

Participants will have up to 6 months to complete all study procedures, from the time the informed consent is signed up to the completion of all study procedures. The number and type of visits (inpatient vs. outpatient) for each group are as follows:

Cannabis Users:

Outpatient Visits OP Visit 1:	MRI, MJ administration & performance session 1 at BPRU Completion of self-report measures
Inpatient (IP) Stay (4	days, 3-nights)
· · · · · · · · ·	MJ administration & performance session 2 at BPRU Admission to Bayview CRU
IP Day 1-4:	Completion of daily self-report measures & Monitored MJ abstinence
IP Day 4:	Completion of self-report measures C11-OMAR PET scan CRU discharge
Controls:	
Outpatient Visits	

Visit 1:

MRI & performance session 1 at BPRU

Completion of self-report measures

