- present a MJ-negative urine sample at screening and prior to study procedures.

Exclusion Criteria: Women will be excluded if pregnant, breast feeding, or planning pregnancy; have amenorrhea, or menstrual cycle dysfunction. Other exclusion criteria are:

- 5th grade reading level as determined by the Shipley-2 vocabulary score < 18 or by Rapid Estimate of Adult Literacy in Medicine (REALM Health Literacy Test),
- Current DSM-5 mood or anxiety disorder;
- Current DSM-5 alcohol or substance use disorder (excluding MJ or nicotine)
- Illicit drug use in last 30 days or positive urine test for illicit drugs (excluding MJ for MJ users)
- Using MJ under the guidance of MD;
- History of seizures, closed head trauma;
- BMI <18 or >35;
- Clinically-significant abnormality on ECG;
- unstable hypertension (BP > 150/90);
- conditions preventing MRI (implanted metal, claustrophobia)
- significant anatomical abnormalities on MRI (e.g., enlarged ventricles, brain lesions);
- Use of prescribed medications in last 3 months; over the counter drugs or herbal supplements which may be counter indicated as determined by study physician may also be excluded
- Have had research related exposure to ionizing radiation that in combination with the study's estimated radiation exposure would result in a cumulative exposure that exceeds recommended exposure limits of 5 rem per year.
- Presence or history of drug allergy, or allergic disease diagnosed and treated by a physician.
- any serious medical condition in whom participation is contraindicated.

To determine eligibility, the medical records will be reviewed by study physicians, and psychological assessments and full inclusion/exclusion criteria will be reviewed by Drs. [name] or [name].

6. Drugs/ Substances/ Devices

- a. The rationale for choosing the drug and dose or for choosing the device to be used.
- b. Justification and safety information if FDA approved drugs will be administered for non-FDA approved indications or if doses or routes of administration or participant populations are changed.
- c. Justification and safety information if non-FDA approved drugs without an IND will be administered.

Marijuana (MJ).

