The effects of MJ on an unborn fetus are unknown but are potentially harmful. Women who are pregnant, planning to become pregnant or nursing will be excluded from study participation. Women of child bearing potential must use an effective non-hormonal form of birth control and will have urine pregnancy tests at screening and prior to all procedures; only women with a negative pregnancy test may participate.

PET radiotracer:

¹¹C-OMAR (4-cyano-1-(2,4-dichlorophenyl)-5-(4-methoxyphenyl)-N-(piperidin-1-yl)-1Hpyrazole-3-carboxamide), previously JHU75528, is a CB1R PET radiotracer. It is an analog of the CB1R antagonist/inverse agonist rimonabant. ¹¹C-OMAR was developed, synthesized and first tested in humans at the JHU PET center^(8, 45, 46), and will be used in the proposed studies under IND 76,698 (effective date: 4/20/07), which is held by [name] (Co-I on this protocol). A single dose of approximately 370-1110 MBq of [¹¹C]-OMAR (approximate mass dose of 5 to 14 micrograms) will be administered during the PET scanning procedure by intravenous bolus administration. Each participant will receive a single intravenous injection of [¹¹C]-OMAR.

¹¹C-OMAR is the appropriate radiopharmaceutical for our studies. It has excellent test-retest reproducibility⁽⁹⁾, and has been used successfully and safely in PET studies in alcohol dependent subjects⁽⁵⁶⁾, post-traumatic stress disorder patients⁽⁶¹⁾, schizophrenic patients⁽⁸⁾ and more recently in male cannabis users⁽⁴³⁾.

7. Study Statistics

- a. Primary outcome variable.
- b. Secondary outcome variables.
- c. Statistical plan including sample size justification and interim data analysis.
- d. Early stopping rules.
 - N/A

Derivation of outcome variables. There is no appropriate, reliable reference region for ¹¹C-OMAR due to the widespread distribution of CB1R in human brain. BP_{ND} (non-displaceable binding potential which requires a measure of absolute non-specific binding) is not appropriate for quantification of this radioligand. Volumes of Interest (VOI) will be generated by spatially normalizing⁽⁸³⁾ a standard VOI template⁽⁸⁴⁾ to individual

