MRI. The MRI does not involve any radiation exposure, but does involve exposure to magnetic fields. Although scientists do not know a great deal about the possible long-term effects of exposure to magnetic fields, the risks of the MRI scanning procedure are presumed to be minimal. Because the MRI instrument contains a powerful magnet, it could be painful if subjects have any metal objects in or on their body; Subjects who report metal in their body are excluded from participation. At-risk subjects (e.g., metalworkers) who may have metal in their eye will also complete a skull x-ray to determine presence of metal prior to the MRI exam (see below). Some people find the MRI unpleasant or claustrophobic.

MRIs will be reviewed by a faculty neuroradiologist, who may identify brain abnormalities (incidental findings), some of which may be clinically significant. These MRI results only identify "incidental findings" as the research MRI is not a full diagnostic MRI. One of the study Physicians will contact the participant and discuss the nature of the findings (e.g. benign, congenital abnormalities etc.) if it is not exclusionary, and if results are clinically significant, will recommend that the participant see his/her physician and if needed refer the participant to a physician. Disclosure of these incidental findings to the participant may be distressing to the participant.

Skull x-ray. As indicated in the MRI procedures, participants may be asked to undergo two skull x-rays to determine the participant has not metal in their skull. This is a standard safety procedure employed by the Johns Hopkins MRI staff to verify it is safe for the participant to enter the MRI area. If participants undergo the skull x-ray there will be an additional 0.01 rem of radiation exposure to the participant.

PET and Radiologic Procedures. Studies that employ PET are approved by the Johns Hopkins University IRB and the Federal Drug Administration (FDA). Subjects will undergo one PET imaging session using the CB1R radiotracer ¹¹C-OMAR. Use of ¹¹C-OMAR PET in current protocol will be under IND# 76,698 (effective date: 4/20/07), which is held by one of the PIs, [name]. Potential risks are detailed below.

1. *Catheters:* All participants will have two catheters, one venous and one arterial, placed prior to the start of each PET scan. The venous catheter will be inserted into a vein of one arm for

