the injection of the radiotracer. The arterial catheter will be inserted into a radial artery of the other arm by an anesthesiologist for rapid withdrawal of blood specimens; up to 40 blood samples (a total blood volume of approximately 150 mL) will be collected for metabolite and radioactivity analysis of the radiotracer.

- 2. Lidocaine. Lidocaine, a local anesthetic, is administered prior to arterial catheter placement. There is the possibility of an allergic reaction following the topical placement or the injection of the lidocaine. Lidocaine will not be administered to participants with known allergy to lidocaine. Lidocaine may cause drowsiness, tremors, and decreased respirations for a few hours after administration. The maximal amount of lidocaine the participant will receive in this study is 10% of the maximal recommended dose and 5% of the dose at which any side effects (such as drowsiness or tremors) would be expected. Therefore, side effects from lidocaine are unlikely.
- 3. Radiotracer. Only high specific activity ¹¹C-OMAR (20 mCi) is being administered in this study. Each participant will receive approximately 740 MBq of ¹¹C-OMAR (mass dose of 0.14 micrograms/kg) during the PET scanning procedure as a bolus injection. This is a tracer dose of drug; therefore, no behavioral or adverse effects of the radiotracer are anticipated. There is a low risk of an allergic reaction following the injection of the radiotracer. [name] has extensive experience with ¹¹C-OMAR under IRB approved protocols NA_00009703,NA_00026434, and NA_00086242. There were no significant side effects or adverse experiences reported during prior studies in healthy control subjects, subjects with schizophrenia, PTSD or alcohol dependence^(8, 56, 61). However, the most common side effects reported with these types of drugs—such as Rimonabant—may include nausea, altered mood, depression, anxiety, dizziness, headache, euphoria, fatigue, and insomnia.

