- 4. Radiation exposure. A tracer dose of 20 mCi (~740 MBq) is delivered in the PET scan and results in a maximum of 0.227 rem effective dose radiation exposure. From the PET transmission scan, participants receive an additional 0.0026 rem of external radiation exposure. Thus the total radiation exposure from the one PET scan will be about 0.23 rem. If participants are required to have the skull x-rays performed to verify it is safe for the participant to enter the MRI area, the radiation exposure will increase by 0.01 rem. Thus, the total possible maximum amount of radiation exposure from the combined internal and external sources of radiation in this study will be about 0.24 rem, which is below the allowable annual radiation exposure limit of 5 rem per calendar year set by JHU. The amount of radiation exposure is also within the limits set forth by 21CFR361.1.
- 5. Women for child bearing potential: To avoid unknown risks for the fetus, women of child bearing potential must use an effective non-hormonal form of birth control and will have urine pregnancy tests at screening and prior to all procedures; only women with a negative pregnancy test may participate.
- 6. Other risks. Several additional risks occur throughout the course of the PET study. PET risks include a risk of pain, bleeding or infection from the catheters used for PET scan procedures. In rare cases, fainting or infection could occur.

For MJ users only: MJ withdrawal: Abstinence after chronic daily use or near daily use of MJ is associated with MJ withdrawal discomfort that includes increases in anxiety, depression, irritability, anger, sleep problems, and decreased food intake and weight loss⁽³⁴⁻³⁷⁾. In a subset of MJ users, blood pressure can significantly increase during MJ abstinence ⁽⁸⁸⁾. Since this is a focus of the study, and we will be selecting individuals that have shown 2 or more symptoms in the past, it is likely participants will experience some of these symptoms. These symptoms are time delimited, not associated with severe health consequences, and typically resolve on their own within 2 weeks.

Controlled MJ administration.

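### The stated maximum radiation exposure of about 0.24 rem is worked out at 740 MBq and does not bound the 370-1110 MBq range given in section 6

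*Combined protocol and SAP*

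**What the plan says.** The combined protocol and SAP states the injected activity in several places.

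- Section 4, PET Scan Procedures (Transmission and emission scan): "an intravenous injection of approximately 20 mCi of" the tracer.
- Section 6, PET radiotracer: "A single dose of approximately 370-1110 MBq of" the tracer. The same paragraph adds: "Each participant will receive a single intravenous injection of" it.
- Section 8, Risks (Radiotracer): "Each participant will receive approximately 740 MBq of" the tracer, with 20 mCi given just before.
- Section 8, Risks (Radiation exposure item): "A tracer dose of 20 mCi (~740 MBq) is delivered in the PET scan and results in a maximum of 0.227 rem effective dose".

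The Radiation exposure item then adds 0.0026 rem for the transmission scan and, if skull x-rays are needed, 0.01 rem. It concludes that the "total possible maximum amount of radiation exposure from the combined internal and external sources of radiation in this study will be about 0.24 rem" and compares this with an annual limit of 5 rem.

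The number of scans is not in doubt. Section 8 (PET and Radiologic Procedures) says: "Subjects will undergo one PET imaging session using the CB1R radiotracer".

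The exclusion criteria in section 5, and the Radiation paragraph in section 8b, exclude anyone whose earlier research exposure combined with the study's "estimated radiation exposure would result in a cumulative exposure that exceeds recommended exposure limits of 5 rem per year".

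**The concern.** A figure described as the greatest exposure possible in the study should hold for every activity the protocol permits. This one is built on 20 mCi, whereas section 6 gives a range whose upper end is 1.5 times that activity (1110/740). As written, a participant could be injected within the section 6 range and receive more than the stated maximum.

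At stake is the accuracy of a safety statement. It is the only whole-study radiation total that the protocol gives, and it concerns healthy volunteers who have no direct benefit from taking part. It is also the figure available for the cumulative-exposure check in sections 5 and 8b.

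**Working it through.** **Inputs.**

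- Tracer: 0.227 rem at 20 mCi, about 740 MBq (section 8, Radiation exposure).
- Transmission scan: 0.0026 rem (same item).
- Skull x-rays, if needed: 0.01 rem (same item, and the Skull x-ray paragraph of section 8).
- Activity range: 370-1110 MBq, one injection (section 6, PET radiotracer).
- Annual limit: 5 rem (section 8, Radiation exposure; sections 5 and 8b).
- Assumption, not in the documents: effective dose is linear in injected activity, and the transmission-scan and x-ray doses do not depend on it.

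**Reproducing the protocol's figures.** PET scan: 0.227 + 0.0026 = 0.2296 rem, stated as about 0.23. With skull x-rays: 0.2296 + 0.01 = 0.2396 rem, stated as about 0.24. Both agree.

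**Where 740 MBq lies in the range.** At 37 MBq per mCi (740/20), 370, 740 and 1110 MBq are 10, 20 and 30 mCi. The midpoint is (370 + 1110)/2 = 740 MBq. The stated maximum is therefore computed at the centre of the section 6 range.

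**Whole-study total across the range.** Total = 0.227 × (activity/740) + 0.0026 + 0.01.

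| Activity | Tracer (rem) | Total with x-rays (rem) | Share of 5 rem |
|---|---|---|---|
| 370 MBq | 0.1135 | 0.1261 | 2.5% |
| 740 MBq | 0.2270 | 0.2396 | 4.8% |
| 1110 MBq | 0.3405 | 0.3531 | 7.1% |

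The ratio of top to stated maximum is 0.3531/0.2396 = 1.47.

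**Effect on the exclusion rule.** A volunteer is excluded when prior research exposure plus study exposure exceeds 5 rem. With the stated figure, the cut-off for prior exposure is 5 − 0.2396 = 4.760 rem. With the figure at 1110 MBq, it is 5 − 0.3531 = 4.647 rem. The decision differs only for prior exposure between about 4.65 and 4.76 rem in the year.

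**The case against.** The strongest defence is that the word maximum refers to procedures and not to activity. In the Radiation exposure item it comes directly after the optional skull x-rays, so it can be read as the worst case with x-rays included, at an activity that the same item states openly. Every procedural and risk statement gives about 20 mCi or 740 MBq. Section 6 is the only outlier, and 740 MBq is its exact midpoint, so the statements may be a nominal activity beside a permitted range.

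Much of this stands. The activity statements need not be in outright conflict. But the label is for the whole study and for combined internal and external sources, and no section clearly caps the injection at 740 MBq. If 740 MBq is nominal, a maximum has to be taken at the top of the range. If about 740 MBq is what every participant receives, the section 6 range does not describe what is done. The text needs reconciling on either reading. The word maximum before 0.227 rem does not help, because that value is given as the result of 20 mCi.

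It is also fair to say that 0.35 rem appears nowhere in the documents and depends on linear scaling of one value whose conservatism cannot be judged.

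A reader might infer more than the documents support:

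- **That the protocol's addition is wrong.** It reproduces exactly.
- **That the range is a total over several scans.** There is one injection and one PET session.
- **That an exposure limit is breached.** Even at the top of the range the total is about 7% of 5 rem. The protocol also cites limits in 21CFR361.1 but does not state them, so that claim can be neither confirmed nor disputed here.
- **That the tracer mass statements conflict as well.** At 0.14 micrograms/kg, the 5 to 14 micrograms in section 6 correspond to body weights of 5/0.14 = 36 kg to 14/0.14 = 100 kg, so they are compatible.

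**Conclusion.** The point holds as an inconsistency in a stated safety figure. About 0.24 rem is correct at 740 MBq, but it does not bound the activity range in section 6. Under linear scaling the total at 1110 MBq would be about 0.35 rem, 47% above the stated maximum.

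The practical weight is very small. The conclusion that exposure is below 5 rem is unchanged. Sections 5 and 8b refer to the study's estimated exposure and do not themselves require an upper bound; that they would use the 0.24 rem figure is an inference from its being the only whole-study total. Even so, eligibility would differ only within a band of prior exposure 4.760 − 4.647 = about 0.11 rem wide. The trial's outcomes and analyses do not depend on the figure. The mismatch between the figure and the range is plain from the text; only the size of the excess rests on the linearity assumption.

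**What to change.** Reconcile the injected activity in section 4 (PET Scan Procedures), section 6 (PET radiotracer) and section 8 (Radiotracer and Radiation exposure). Where a nominal activity is meant, say so. Compute the stated maximum at the highest activity the reconciled protocol allows, and use that one figure in section 8 and in the cumulative-exposure check of sections 5 and 8b. Which activity is right is for the sponsor and investigators to settle.

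The cost is a short text correction and, depending on the outcome, one recomputed number. No new procedure, data or analysis is needed.
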